4.1 Eligibility Verification/Registration

Before subjects are registered to the study, an eligibility checklist (Appendix E) must be completed to verify the subject meets the eligibility criteria and may be used as source documentation if it has been reviewed, signed, and dated prior to registration by the treating physician. The eligibility check list will be maintained in the study file.

Date of Enrollment: Defined as the date of the start of study treatment / first study related intervention.

Study personnel from UNMC will provide the UNMC Fred & Pamela Buffett Cancer Center PRMS office (ZIP 6805) a copy of the signed and dated consent form for each UNMC subject enrolled in the protocol within 24 hours that includes the following information:

- Protocol Number
- Patient Identification: Patient's name UNMC/NMC medical record number
- Patient demographics: gender, birth date (mm/dd/yyyy), race, ethnicity,
- New CTRP reporting requirements: Patient zip code/country (if not USA) and primary method of payment information

4.2 Pathology Requirements

Pathological materials are to be submitted and reviewed at UNMC confirming a diagnosis of DLBCL or transformed DLBCL.

4.3 Instructions for Patients Who Do Not Start Assigned Protocol Treatment

If a consented patient does not receive any assigned protocol treatment, baseline data will still be collected and must be submitted according to the instructions in the protocol. Document the reason for not starting protocol treatment on one of the baseline forms.

Section 5.0 Treatment Plan of Research Design:

This is a single-center Phase IIa study evaluating the safety and tolerability of umbralisib and Ibrutinib as well as the response and event free survival of this regimen in patients with relapsed or refractory diffuse large B-cell lymphoma (DLBCL). There will be 3 treatment groups given a maximum of one year (12 months) of therapy.

5.1 Pre-treatment Evaluations Standard of Care (SOC)

Within 21 days prior to the Date of Enrollment, date of the start of study treatment / first study related intervention (unless otherwise specified below). No tests or procedures are conducted solely for the purposes of research to determine subject eligibility.

- History and physical
- Informed Consent
- CBC, diff, platelets, CMET, LDH
- Hepatitis B (HBV) or C (HCV) serology
- Serum pregnancy test (if applicable) within 14 days of first study-related treatment date.
- Height and weight
- Vital signs, including blood pressure
- Performance Status
- EKG
- PET/CT baseline radiologic evaluation; NOTE for f/u if a Deauville 3 (CR) is achieved then CT chest, abdomen and pelvis with contrast may be used. Further PET/CT scans are optional at the investigators discretion.
- Mandatory research peripheral blood (20 mL) for cell free DNA assessment and T-cell characterization will be collected in an EDTA tube pretreatment (day of biopsy or initiation of treatment), day 8, 1 month (+/- 3 days) and 10mL at subsequent radiographic response assessments, after cycle 2, 4, 6, 9, and 12. (+/- 7 days). After Month 12, efficacy assessments should occur at the investigators discretion with collection of a research blood sample only if feasible. Should the patient consent any leftover peripheral blood collected for research will be stored at UNMC for future IHC and DNA unspecified research use.
- Optional Research Samples (Appendix G):
 - Should the patient consent, 3 additional optional lymph node biopsies for molecular profiling will be obtained at days 0 (pre-treatment; core biopsy), day 8 (FNA) and end of treatment (progressive disease, toxicity, or end of study—1 year; core biopsy) to evaluate the baseline characteristics and dynamic shifts in mutational landscape, transcriptional signatures and intracellular signaling cascades in primary tumor cells as well as assessment of comparative serologic response to radiographic assessments of response.

Specimens submitted, by patients who consent to the additional specimen collection, will be processed to maximize their utility for future unspecified research projects and may include, but not limited to, extraction of plasma, serum, DNA and RNA. Specimens will be archived with appropriate safeguards to ensure an efficient system for the prompt linkage and retrieval of the stored samples with the subject's study records.

Specimens from patients who consented to allow their specimens to be used for future IRB, TG Therapeutics, and Janssen Scientific LLC approved research studies, including residuals from the currently defined research studies, will be retained in an UNMC-designated central repository. If the patient agrees to let the samples be kept for future research, the samples will be kept until they are used up or destroyed. Most future research studies will focus on cancer, some research projects may also include other diseases, such as heart disease, diabetes or Alzheimer's disease. This may also include research on inherited traits. All future IRB, TG Therapeutics, and Janssen Scientific LLC approved research studies will be conducted in accordance with the requirements set forth in the UNMC Human Tissue Use and Transfer Policy (policy #8013).

5.2 Treatment Grouping and Dosing

Medicare qualifying research related combination chemotherapy:

Stratification will be performed on a 1:1:1 basis to Group A, B or C by willingness to consent to optional biopsies. The first 3 patients will be directly enrolled into cohort C regardless of decision to be included in the optional biopsy portion of the study.

Group A (consented to optional biopsies; 6 patients): umbralisib 800 mg PO daily on Days 1-8; then umbralisib 800 mg oral daily and Ibrutinib 560 mg oral daily

Group B (consented to optional biopsies; 6 patients): Ibrutinib 560 mg PO daily Days 1-8; then umbralisib 800 mg PO daily and Ibrutinib 560 mg PO daily

Group C (deferred consent to optional biopsies or consented to optional biopsies; 12 patients): umbralisib 800 mg PO daily and Ibrutinib 560 mg PO daily

All subjects will receive a maximum of 52 weeks of oral (self-administered) therapy. To provide a means of ensuring oral routes of medication adherence of patients while participating in a clinical trial **Appendix F** "Oral, Sublingual, and/or Buccal Route Medication Adherence Standard Procedure (V 1.0 11-25-2013)" will be followed.

No routine prophylactic antiemetics or pre-medications should be given outside of protocol requirements. However, these medications may be administered for symptoms when they occur, and may be given prophylactically afterwards. Appropriate anti-emetic regimens should be based on the recommendations made by the NCCN guidelines (SOC). http://www.nccn.org/professionals/physician_gls/PDF/antiemesis.pdf

5.2.1 Guidelines for Administration of umbralisib

- Method of Administration: Umbralisib 4 tablets each 200mg = 800mg will be administered orally once daily.
 Umbralisib should be taken in the morning. (NOTE: After cycle 2 if no CTE have been seen then the patient can have the option to take umbralisib and Ibrutinib dosing together at the same time of day).
- Umbralisib tablets should be swallowed whole with a full glass (approximately 8 ounces) of water. umbralisib tablets should NOT be crushed or chewed.
- Potential Drug Interactions: No Drug Interactions have been reported to date.
- Pre-medications: None

Umbralisib will be self-administered (by the patient). Tablets should be taken at approximately the same time each morning with food. Patients should be instructed to swallow the tablets whole and should not chew or crush them. If a dose of umbralisib is missed, it should be taken as soon as possible on the same day. If a dose is missed, it should not be replaced. If vomiting occurs, no attempt should be made to replace the vomited dose. Study drug compliance should be reviewed with the patient at the beginning of each new treatment cycle. Missed doses should be documented. (Appendix F "Oral, Sublingual, and/or Buccal Route Medication Adherence Standard Procedure (V 1.0 11-25-2013)"

5.2.2 Guidelines for Administration of Ibrutinib

- Method of Administration: Ibrutinib 4 capsules each 140mg = 560mg will be administered orally once daily.
 Ibrutinib should be taken in the evening. (NOTE: After cycle 2 if no CTE have been seen then the patient can have the option to take umbralisib and Ibrutinib dosing together at the same time of day).
- Ibrutinib capsules should be swallowed whole with a full glass (approximately 8 ounces) of water. Ibrutinib capsules should not be opened, chewed or dissolved.
- Potential Drug Interactions: Avoid co-administration with strong or moderate CYP3A inhibitors and consider
 alternative agents with less CYP3A inhibition. Concomitant use of strong CYP3A inhibitors which would be
 taken chronically (e.g., ritonavir, indinavir, nelfinavir, saquinavir, boceprevir, telaprevir, nefazodone) is not
 recommended. For short-term use (treatment for 7 days or less) of strong CYP3A inhibitors (e.g., antifungals

and antibiotics) consider interrupting ibrutinib therapy until the CYP3A inhibitor is no longer needed [see Drug Interactions (7.1)]. Reduce ibrutinib dose to 140 mg if a moderate CYP3A inhibitor must be used (e.g., fluconazole, darunavir, erythromycin, diltiazem, atazanavir, aprepitant, amprenavir, fosamprevir, crizotinib, imatinib, verapamil, and ciprofloxacin) [see Drug Interactions (7.1)]. Patients taking concomitant strong or moderate CYP3A inhibitors should be monitored more closely for signs of ibrutinib toxicity.

- Also avoid grapefruit and Seville oranges during treatment, as these contain moderate inhibitors of CYP3A and can alter ibrutinib pharmacokinetics.
- For patients with mild liver impairment (Child-Pugh class A), the recommended dose is 140 mg daily (one capsule). Avoid the use of ibrutinib in patients with moderate or severe hepatic impairment (Child-Pugh classes B and C) [see Use in Specific Populations (8.7) and Clinical Pharmacology (12.3)]
- Pre-medications: None

Ibrutinib will be self-administered (by the patient). Capsules should be taken at approximately the same time each evening with food. Patients should be instructed to swallow the capsules whole and should not chew, break or crush them. If a scheduled dose of Ibrutinib is missed it should be taken as soon as possible on the same day with a return to the normal schedule the following day. Extra capsules of ibrutinib should not be taken to make up for the missed dose. If vomiting occurs, no attempt should be made to replace the vomited dose. Study drug compliance should be reviewed with the patient at the beginning of each new treatment cycle. Missed doses should be documented. (Appendix F "Oral, Sublingual, and/or Buccal Route Medication Adherence Standard Procedure (V 1.0 11-25-2013)"

5.3 Supportive medications and procedures

The following treatments are prohibited while on clinical trial: other investigational drug treatments or study participation, radiation therapy (except as described in section 3.2 Exclusion Criteria #1), hormonal therapy for cancer, cancer immunotherapy or other biologic therapy excluding trial drugs.

No glucocorticoids may be administered outside of protocol requirements for premedication or AE
management, except low doses of steroids stabilized at ≤ 10 mg per day of prednisone or equivalent, and
started at least 7 days prior to study entry.

Patients should receive full supportive care while on this study. This includes blood product support, antibiotic treatment, and treatment of other newly diagnosed or concurrent medical conditions. All blood products and supportive care concomitant medications such as antidiarrheals, analgesics, and/or antiemetics received from the first day of study treatment administration until 30 days after the final dose will be recorded in the medical records.

Neutropenia: Granulocyte colony stimulating factor (G-CSF; filgrastim or pegfilgrastim) may be used during the course of the study at the investigator discretion. The drug(s) should be used at a dose/schedule specified in the package insert.

Antiemetics: Umbralisib and ibrutinib are considered to be of low emetogenic potential that may be adequately prevented with prochlorperazine. Other antiemetics may be used at the discretion of the treating physician if nausea and/or vomiting is not adequately controlled/prevented. Appropriate anti-emetic regimens should be based on the recommendations made by the NCCN guidelines (SOC). http://www.nccn.org/professionals/physician_gls/PDF/antiemesis.pdf

Tumor Lysis Syndrome: Subjects at risk for tumor lysis syndrome in the opinion of the treating investigator, prophylaxis with allopurinol or institutional standards should be considered. Patients felt to be at risk for tumor lysis syndrome by the treating investigator will be monitored at least for the first 3 days of cycle 1 of therapy.

Pneumocystis Jiroveci Pneumonia (PCP) and Viral Infections: Prophylactic treatment with pneumocystis jiroveci pneumonia (PCP) and antiviral therapy should be considered. Recommended anti-viral prophylaxis is with Valtrex 500 mg daily or Acyclovir 400 mg BID or equivalent. Recommended PCP prophylaxis is with Dapsone 100 mg daily. Final choice of PCP and anti-viral prophylactic therapy is per investigator discretion. If PCP or anti-viral therapy is not

Page 18 of 65

tolerated, alternate to a different PCP or anti-viral therapy, discontinue, or reduce dose/schedule as per investigator discretion.

Blood Product Support: Blood products should be utilized as clinically warranted and following institutional policies and recommendations.

5.4 Duration of therapy

In the absence of treatment delays due to adverse event(s), treatment should continue unless one of the following criteria applies:

- Disease progression or inter-current illness that prevents further treatment.
- Patient decides to withdraw from the study, or changes in the patient's condition render the patient unacceptable for further treatment in the judgment of the investigator.
- One year of therapy

5.5 Follow-up Evaluations Course Assessment Schedule

A cycle is 28 days of treatment with any oral agent regardless of group assignment. Response assessment will be done after cycles 2, 4, 6, 9, and 12 (+/- 7 days). After Month 12, efficacy assessments should occur at the investigators discretion.

We will continue to routinely monitor safety in regards to serious adverse events as well as for toxicity trends that may be of concern.

The reason for study removal and the date the patient was removed must be documented in the Case Report Form.

Patients who discontinue therapy due to an adverse event should be followed until disease progression.

5. 6 Toxicity Assessments and Dose modifications

5.6.1 Definitions of Cumulative Toxicity Event (CTE)

For this protocol, cumulative toxicity event (CTE) will be defined as follows: an adverse event attributed (definitely, probably or possibly related) to the study treatment and meeting following criteria within cycles 1 to 4. AE grading and assignment of attribution require documentation by medical personnel who are directly involved in the clinical care of protocol subjects.

Toxicity	Definition					
Hematologic	Either:					
	1. Grade 4 hematologic toxicities (attributed to either or both drugs) defined as:					
	b. Grade 4 thrombocytopenia (platelets < 25 K/μL)					
	c. Grade 4 neutropenia (absolute neutrophil count (ANC) < 0.5)					
	2. Grade 3 thrombocytopenia or neutropenia that results in a > 7 day delay in either					
	drug.					
Non-hematologic	Either:					
_	1. ≥ Grade 3 as per NCI Common Terminology Criteria for Adverse Events v4.03*					
	(attributed to either or both study drugs).					
	2. One week or greater delay in initiating any cycle day 1 due to continued drug-					
	related toxicity.					

^{*}Grade 3 nausea, vomiting, or diarrhea with maximal supportive treatment(s) will be considered a CTE. Fatigue Grade >/= 3 considered to be due to treatment (definitely, probably, or possibly related) will be considered a CTE.

Patients should be assessed clinically for toxicity at each visit using the NCI CTCAE v4.03 (http://evs.nci.nih.gov/ftp1/CTCAE/CTCAE) grading scale. The study will be terminated if a cumulative toxicity event (CTE) occurs in: ≥2/first 4; ≥4/first 8; or if more than 12 patients when the last (24th) evaluable patient has completed UNMC IRB#345-16 Protocol Version 4.2 Dated 07Oct2019

cycle 4. If a patient has progression of disease or is removed from study not related to a CTE after completion of 2 cycles but less than 4 cycles the patients safety evaluation will be included, but noted appropriately. If the patient receives less than 2 cycles than the patient will not be included and noted, but will not be replaced.

Dosing will occur only if a patient's clinical assessment and laboratory test values are acceptable.

Dose modification and or intervention with supportive care recommendations for umbralisib, and ibrutinib are provided below, however final discretion lies with the treating investigator in regards to more or less aggressive intervention, which specific investigational agent (or if both agents) needs to be reduced, and actual dose reductions, as well as the number of dose reductions.

5.6.2 Treatment Initiation/Continuation:

Starting a new cycle or continuing treatment after a CTE should be administered per protocol provided that:

- Absolute neutrophil count ≥ 1000/uL and platelet count ≥ 50,000/uL
- Recovered from grade 3-4 non-hematologic toxicity to grade 1 or baseline.
- Treatment may be delayed to recover from toxicity or per investigator discretion.
- No clinical or radiographic evidence of disease progression.

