2.2.3 Clinical activity and Safety of ibrutinib

Ibrutinib was tested in a phase I, multicenter, open-label, dose escalation study in patients with recurrent NHL.(14) The objectives included studying the safety profile of ibrutinib, identifying the maximum tolerated dose (MTD) and optimal dosing schedule, and characterizing efficacy, pharmacokinetics, and pharmacodynamics. A minimum of 6 subjects per cohort received 1 of 5 escalating dose levels of ibrutinib between 1.25 and 12.5 mg/kg for 28 consecutive days in a 35-day cycle. There was a pre-specified objective of escalating 3 dose levels above that which achieved full BTK occupancy based on the fluorescent probe assay.

A total of 66 patients were evaluated in this study. Two additional cohorts received a continuous ibrutinib dose of 8.3 mg/kg without a 7-day rest and a fixed continuous dose of 560 mg/day. Full BTK occupancy was achieved with doses ≥2.5 mg/kg/day. A dose of 12.5 mg/kg/day was the highest dose cohort evaluated. There were 2 dose-limiting toxicities (DLTs) (Grade 2 neutropenia [2.5 mg/kg/day] and Grade 3 hypersensitivity [8.3 mg/kg/day]) in separate cohorts. The maximum tolerated dose (MTD) of ibrutinib in subjects with B-cell malignancies was not established in this study. Five of 15 subjects with DLBCL (33%) achieved objective responses, 2 CRs and 3 partial responses (PRs). The median

time on treatment was 8 weeks (range: 2 to 98 weeks). Median PFS was 2.5 months (range: 0.7 to 4.6 months) and the median follow-up time was 3.5 months (range: 0.8 to 22.5 months).

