⁷ The study will be terminated if a cumulative toxicity event (CTE) occurs in: ≥2/first 4; ≥4/first 8; or if more than 12 patients when the last (24th) evaluable patients has completed cycle 4. If a patient has progression of disease or is removed from study not related to a CTE after completion of 2 cycles but less than 4 cycles the patient's safety evaluation will be included, but noted appropriately. If less than 2 cycles than the patient will not be included and noted, but will not be replaced. The stopping rule would be appropriately adjusted if this were to occur.

Page 28 of 65

⁸ Optional biopsies obtained via US or CT guided biopsy of accessible lymph node: Day 0 (pre-treatment; core biopsy), day 8 (fine needle aspiration) and end of treatment (progressive disease or end of study treatment—1 year; core biopsy). At the discretion of the treating investigator, patient on non-coumadin based anticoagulation should have anticoagulant held for biopsy.

⁹Mandatory research peripheral blood samples will be collected in a 20 ml EDTA tube pretreatment (day of biopsy or initiation of treatment; (+/- 3 days)), day 8 (+/- 3 days), 1 month (+/- 3 days) and 10 mL at subsequent radiographic response assessments, after cycle 2, 4, 6, 9, and 12. (+/- 7 days). After Month 12, efficacy assessments should occur at the investigators discretion with 10mL EDTA peripheral blood samples obtained ONLY IF FEASIBLE.]

Section 8.0 Drug Formulation and Procurement:

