9.2 Auditing

The UNMC Fred & Pamela Buffett Cancer Center Scientific Review Committee (SRC) will review this protocol on at least an annual basis.

This study will undergo audit on at least a quarterly basis by the UNMC Fred & Pamela Buffett Cancer Center Audit Committee.

Detailed policy and procedures for this section may be reviewed at: http://www.unmc.edu/cancercenter/clinical/prms.html.

Section 10.0 Statistical Considerations

The phase IIa portion will further assess the safety and tolerability and allow a preliminary assessment of the efficacy of the novel combination to provide background for an appropriately powered phase II study. We plan to accrue 24 patients into the phase IIa portion at a micronized dose of 800 mg of umbralisib and 560 mg of ibrutinib. The assessment of toxicity and efficacy will be performed within the entire cohort. To consecutively monitor the safety primary endpoint in the phase IIa portion, we will employ a sequential probability stopping rule for the predefined portion of cycles 1-4. This stopping rule specifies that the study will be terminated if a cumulative toxicity event (CTE) occurs in: $\geq 2/\text{first } 4$; $\geq 4/\text{first } 8$; or if more than 12 patients when the last (24th) evaluable patient has completed the trial have any CTE. This rule has the following stopping probability:

True	5%	10%	15%	20%	25%	30%	35%	40%	50%
toxicity									
rate									
Stopping prob.	0.000	0.000	0.001	0.004	0.016	0.056	0.118	0.243	0.632

A CTE is defined as:

- Grade ≥ 3 non-hematologic (attributed to either or both study drugs)
- Grade 4 hematologic toxicities (attributed to either or both drugs) defined as:
 - Grade 4 thrombocytopenia (platelets < 25 K/μL)
 - o Grade 4 neutropenia (absolute neutrophil count (ANC) < 0.5)
- Grade 3 thrombocytopenia or neutropenia that results in a > 7 day delay in either drug.
- One week or greater delay in initiating any cycle day 1 due to continued drug-related toxicity.

If a patient has progression of disease or is removed from study not related to a CTE after completion of 2 cycles but less than 4 cycles the patient's safety evaluation will be included, but noted appropriately. If less than 2 cycles than the patient will not be included and noted, but will not be replaced. The stopping rule would be appropriately adjusted if this were to occur.

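### The CTE stopping rule leaves out patients with fewer than 2 cycles even if they have already had a CTE, and does not say whether its early looks use treated or evaluable patients

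*Combined protocol and SAP*

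**What the plan says.** Section 5.6.1 defines a CTE as a treatment-attributed event "meeting following criteria within cycles 1 to 4", so an event in cycle 1 qualifies. The study stops if a CTE "occurs in: ≥2/first 4; ≥4/first 8; or if more than 12 patients when the last (24th) evaluable patient" has completed cycle 4. Section 10.0 repeats the boundaries, with a different end point for the last look: "or if more than 12 patients when the last (24th) evaluable patient has completed the trial have any CTE".

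Two sentences deal with patients who leave early. The first keeps a patient who progresses or is "removed from study not related to a CTE after completion of 2 cycles but less than 4 cycles". The second, in Section 5.6.1, reads: "If the patient receives less than 2 cycles than the patient will not be included and noted, but will not be replaced". Section 7.0 (footnote 7) and Section 10.0 shorten the second sentence to "If less than 2 cycles than the patient will not be included and noted, but will not be replaced", and both add: "The stopping rule would be appropriately adjusted if this were to occur". Section 5.6.1 lacks that addition.

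Planned accrual is 24 (Section 10.0). That section also says that toxicity is assessed in the whole cohort.

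**The concern.** The CTE window opens in cycle 1, but a patient must receive 2 cycles to be included. In Section 5.6.1 the exclusion is a sentence of its own, and it contains no exception for a patient who already has a qualifying event. The shorter wording in Sections 7.0 and 10.0 might carry over the restriction to departures unrelated to a CTE. Even then, a patient with a cycle-1 CTE who progresses before completing 2 cycles has left for a reason unrelated to the CTE and is dropped.

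The second gap is the denominator. The word evaluable is attached only to the 24th patient; the 4- and 8-patient looks have no qualifier in any of the three sections.

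Together, these gaps mean that a qualifying event can be missing from the formal count for the primary safety endpoint, and that the reading would be chosen with the data in hand. A smaller consequence is that, with 24 accrued and no replacement, one exclusion means a 24th evaluable patient never exists. The promised adjustment is not specified.

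**Working it through.** **Plan's own figure.** Section 10.0 prints stopping probabilities of 0.004, 0.056, 0.243 and 0.632 at true CTE rates of 20, 30, 40 and 50%. These do not follow from the written boundaries (at least 2 of 4, at least 4 of 8, at least 13 of 24). With q the rate that the rule sees:

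- Look at 4: 1 − (1−q)^4 − 4q(1−q)^3. At q = 0.40: 1 − 0.1296 − 0.3456 = 0.5248.
- Look at 8, after 0 or 1 event at the first look: 0.3456 × P(at least 3 of the next 4) + 0.1296 × P(4 of the next 4) = 0.3456 × 0.1792 + 0.1296 × 0.0256 = 0.0652.
- Look at 24: the same recursion gives 0.0117.

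| True rate | Look at 4 | Look at 8 | Look at 24 | Total | Printed |
|---|---|---|---|---|---|
| 20% | 0.181 | 0.012 | 0.000 | 0.193 | 0.004 |
| 30% | 0.348 | 0.036 | 0.001 | 0.386 | 0.056 |
| 40% | 0.525 | 0.065 | 0.012 | 0.602 | 0.243 |
| 50% | 0.688 | 0.082 | 0.035 | 0.805 | 0.632 |

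At 50% the first look alone exceeds the printed total. This is a separate problem. The figures below take the written boundaries as intended and compare with the recomputed totals.

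**Effect of the exclusion.** Let p be the true rate, and f and g the shares of CTE and CTE-free patients who leave before 2 cycles. The documents give neither share for this combination, so all values are assumptions. Section 2.2.3 reports, for single-agent ibrutinib, that the median "time on treatment was 8 weeks (range: 2 to 98 weeks"). Two 28-day cycles are also 8 weeks, so early departure is plausible; this says nothing about CTE patients in particular.

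*Looks on treated patients* (an excluded patient fills a place but adds no event): q = p(1−f). Here g has no effect, and stopping can only become less likely.

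| p | f = 0 | f = 10% | f = 25% | f = 50% |
|---|---|---|---|---|
| 20% | 0.193 | 0.159 | 0.114 | 0.053 |
| 30% | 0.386 | 0.324 | 0.237 | 0.114 |
| 40% | 0.602 | 0.515 | 0.386 | 0.193 |

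*Looks on evaluable patients*: q = p(1−f) / [p(1−f) + (1−p)(1−g)]. At p = 40%:

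| f | g | q | Stopping probability |
|---|---|---|---|
| 10% | 0 | 0.375 | 0.547 |
| 25% | 0 | 0.333 | 0.457 |
| 50% | 0 | 0.250 | 0.285 |
| equal | equal | 0.400 | 0.602 |
| 10% | 50% | 0.545 | 0.878 |
| 25% | 50% | 0.500 | 0.805 |

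The evaluable calculation uses 24 evaluable patients at the last look; that look contributes little in every case.

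**Example.** Two of the first 4 treated patients have a CTE, and one of them leaves before 2 cycles.

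- Looks on treated patients: the count is 1, so the trial continues.
- Looks on evaluable patients: there is 1 CTE in 3, and the next evaluable patient decides. If that patient's CTE chance is 20 to 40%, the trial continues with probability 80 to 60%.
- Every CTE counted: the count is 2 of 4, so the trial stops.

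**Last look with fewer patients.** With 20 evaluable, keeping the boundary at more than 12 adds 0.0004 at 40% and 0.0024 at 50%. A boundary of more than half (at least 11) adds 0.0108 and 0.0281.

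**The case against.** The strongest reply is that this is loose drafting. The exclusion follows a sentence about departures unrelated to a CTE, and the trigger is worded as an event occurring. The natural intent may be to handle patients who were not observed long enough, not to remove an event already seen. A second early CTE could also trip the rule before anyone's 2-cycle status is known. That may well be the intent, but it is not written, and it does not settle the patient with a CTE who then progresses.

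Other points carry weight:

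- The treated-patient reading fits poorly with text that says the patient is not included. A reduced denominator is another possible reading, but it cannot be computed because no boundary is given for 3 or 7 patients.
- A CTE does not by itself end treatment: Section 5.6.2 provides for continuing after one. So f may be small. At f = 5% and g = 0, looks on evaluable patients at 40% give 0.575 against 0.602.
- On evaluable looks the direction is not fixed, and with g above f the written rule stops more often.
- The events are not hidden. Grade 3 or higher events and serious adverse events go to the monitoring committee (Section 9.1.2), and toxicity trends are watched (Section 5.5).

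These points limit the size and the certainty about intent. Neither the whole-cohort statement nor the promised adjustment says that an early CTE counts or who the first 4 and first 8 patients are.

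**Conclusion.** The concern holds. Followed as written, Section 5.6.1 can leave an observed qualifying toxicity out of the formal count, and the undefined looks allow different decisions from the same data. The effect falls mainly on the 4-patient look, which supplies 0.525 of the 0.602 stopping probability at a true 40%. Across the illustrated scenarios at that rate, stopping ranges from 0.19 to 0.88. That spread rests on assumed departure shares and on taking the written boundaries as intended, so it shows sensitivity and does not predict what will happen. The absence of an exception is certain; how often it would matter is not known. The missing 24th evaluable patient is minor, because the last look adds at most 0.035 up to a true rate of 50%. This should be fixed.

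**What to change.** State one rule in Section 5.6.1, Section 7.0 footnote 7 and Section 10.0: *any treated patient with a CTE in cycles 1 to 4 counts as an event and as evaluable, whatever the number of cycles received; only CTE-free patients with fewer than 2 cycles are left out.* Say whether the 4- and 8-patient looks use treated or evaluable patients, and give stopping probabilities for that choice.

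Two smaller changes would help. Take the last look when every treated patient has completed cycle 4 or left, with a boundary fixed in advance for fewer than 24 evaluable (more than half is one option). Report the all-treated CTE rate beside the evaluable rate.

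The cost is a few sentences in three places, with no extra patients or procedures. There is a statistical downside to state. With evaluable looks, leaving out CTE-free early leavers already raises the counted rate, and counting every CTE raises it further:

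| True rate | No exclusions | Written rule, f = 25%, g = 25% / 50% | With fix, g = 25% / 50% |
|---|---|---|---|
| 20% | 0.193 | 0.193 / 0.330 | 0.285 / 0.457 |
| 30% | 0.386 | 0.386 / 0.583 | 0.523 / 0.731 |
| 40% | 0.602 | 0.602 / 0.805 | 0.749 / 0.912 |

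In these scenarios the fix itself adds 0.09 to 0.15. With looks on treated patients, it gives 0.193, 0.386 and 0.602, without that upward shift. The price is that early leavers without a CTE are treated as CTE-free although they were not observed for 4 cycles.
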